9.7 Efficacy Subgroup Analyses

To evaluate the consistency of the efficacy over demographic and other baseline characteristics, subgroup analysis will be performed for the primary endpoint for the subgroups listed in [Table 4](#) below using ITT1.

For subgroup analysis, point estimate and 95% CI for each treatment group as well as point estimate and 95% CI for treatment differences between each ABBV-154 group and placebo group will be presented. No p-value will be provided. If any of the resulting categories for a subgroup factor listed in [Table 4](#) (except age, sex and race), has fewer than 10% of the planned total sample size, subgroup analyses will not be presented for that category.

Table 4. Subgroups for Efficacy Analysis

Subgroup Factor	Categories
Sex	Male, Female
Age	≥ 18 years - < 40 years, ≥ 40 years - < 65 years, ≥ 65 years
Race	White, non-White
Baseline Glucocorticoid Use	Yes or No
Endoscopic Disease Severity	SES-CD < 15, SES-CD ≥ 15
Inadequate Response to adalimumab	Yes or No
Inadequate response to prior anti-TNF biologics	Yes or No

9.8 Efficacy Analyses for ABBV-154 Rescue Therapy

To evaluate the efficacy for ABBV-154 rescue therapy, the following endpoints will be analyzed on ITT3-RES population and AO analysis will be performed:

- Achievement of clinical remission per CDAI at Week 12 and Week 24 after ABBV-154 rescue therapy
- Achievement of clinical remission per SF/AP at Week 12 and Week 24 after ABBV-154 rescue therapy
- Achievement of CR100 at Week 12 and Week 24 after ABBV-154 rescue therapy
- Mean FCP at Week 12 and Week 24 after ABBV-154 rescue therapy
- Mean hs-CRP at Week 12 and Week 24 after ABBV-154 rescue therapy

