Subjects who receive Rescue Therapy, fail to complete glucocorticoid tapering by Week 6, or increase doses of or initiate treatment with aminosaliclates or immunomodulators in the Induction Period will be considered non-responders, regardless of clinical response or endoscopic response (per local read) per the definitions above at Week 12 and will be re-randomized in a 1:1 ratio into 2 ABBV-154 treatment groups in the 12-Week Re-Induction Period as follows:

1. Re-Induction Group 1: Loading dose of 300 mg IV at Week 0, followed by 230 mg SC at Week 2 and EOW;
2. Re-Induction Group 2: Loading dose of 600 mg IV at Week 0, followed by 530 mg SC at Week 2 and EOW.

Subjects who achieve clinical response AND/OR endoscopic response (per local read) at Week 12 of the Re-Induction Period will be re-randomized into the Maintenance Period as described above for subjects achieving clinical response AND/OR endoscopic response (per local read) after Week 12 of the Induction Period. Subjects who do not achieve either clinical response or endoscopic response (per local read) after the Re-Induction Period will be discontinued and will have a follow-up visit scheduled 70 days after last study drug administration.

To determine endoscopic response status for re-randomization into the Maintenance Period, the SES-CD score per local read at Week 12 of the Induction/Re-Induction Period and the SES-CD score per central read at Baseline will be used. In the case of missing data where either clinical response or endoscopic response cannot be determined, subjects will be considered non-responders for the re-randomization criteria evaluation.

Subjects who have an inadequate response at or after Week 4 in the Maintenance Period will be eligible to receive Rescue Therapy with a single dose of ABBV-154 600 mg IV followed by ABBV-154 230 mg SC EOW. Subjects who have received rescue therapy with ABBV-154 for at least 4 weeks and who continue to demonstrate inadequate response may receive additional Rescue Therapy with oral glucocorticoids, aminosaliclates, or immunomodulators. Rescue Therapy options for the Maintenance Period are further described in Section 5.4.

The last dose of study drug will be given at Week 38 of the Maintenance Period. A follow-up visit will be scheduled 70 days after the last study drug administration.

[figure not shown]

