At Week 12 of the Induction Period, subjects who are categorized as clinical non-responders and endoscopic non-responders (per local read) will be re-randomized into the Re-Induction Period. Subjects who receive Rescue Therapy, fail to complete glucocorticoid tapering by Week 6, or increase doses of or initiate treatment with aminosalicylates or immunomodulators in the Induction Period will be considered non-responders, regardless of clinical response or endoscopic response (per local read) per the definitions above at Week 12 and will be re-randomized in a 1:1 ratio into 2 ABBV-154 treatment groups in the 12-Week Re-Induction Period as follows:

- Re-Induction Group 1: Loading dose of 300 mg IV at Week 0, followed by 230 mg SC at Week 2 and EOW;
- Re-Induction Group 2: Loading dose of 600 mg IV at Week 0, followed by 530 mg SC at Week 2 and EOW.

Subjects who achieve clinical response AND/OR endoscopic response (per local read) at Week 12 of the Re-Induction Period will be re-randomized into the Maintenance Period as described above for subjects achieving clinical response AND/OR endoscopic response

(per local read) after Week 12 of the Induction Period. Subjects who do not achieve either clinical response or endoscopic response (per local read) after the Re-Induction Period will be discontinued and will have a follow-up visit scheduled 70 days after last study drug administration.

To determine endoscopic response status for re-randomization into the Maintenance Period, the SES-CD score per local read at Week 12 of the Induction/Re-Induction Period and the SES-CD score per central read at Baseline will be used. In the case of missing data where either clinical response or endoscopic response cannot be determined, subjects will be considered non-responders for the re-randomization criteria evaluation.

[figure not shown]
Subjects who have an inadequate response at or after Week 4 in the Maintenance Period will be eligible to receive Rescue Therapy with a single dose of ABBV-154 600 mg IV followed by ABBV-154 230 mg SC EOW. Subjects who have received rescue therapy with ABBV-154 for at least 4 weeks and who continue to demonstrate inadequate response may receive additional Rescue Therapy with oral glucocorticoids, aminosalicylates, or immunomodulators.

The last dose of study drug will be given at Week 38 of the Maintenance Period. A follow-up visit will be scheduled 70 days after the last study drug administration.

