4.0 Analysis Populations

The following population sets will be used for the analyses.

ITT Populations

ITT population: The ITT Population includes all subjects who were randomized and received at least 1 dose of study drug.

ITT1 population: The subset of the ITT Population who were randomized and received at least 1 dose of study drug in the Induction Period. The ITT1 Population is the primary analysis population for efficacy analyses of the Induction Period.

ITT2 population: The subset of the ITT population who were randomized and received at least one dose of study drug in the Re-Induction Period. The ITT2 Population is the analysis population for efficacy analyses of the Re-Induction Period.

ITT3 population: The subset of the ITT population who received ABBV-154 for 12 weeks before entering the Maintenance Period (including subjects were randomized to ABBV-154 dose groups in the Induction Period and entered the Maintenance Period from the Induction Period OR were randomized to the placebo group in the Induction Period and entered the Maintenance Period from the Re-Induction Period) AND were randomized and received at least one dose of study drug in the Maintenance Period. The ITT3 Population is the primary analysis population for efficacy analyses of the Maintenance Period.

ITT3-RN population: The subset of the ITT population who were enrolled and received at least one dose of study drug in the randomized portion of the Maintenance Period.

ITT3-NRN population: The subset of the ITT population who were enrolled and received at least one dose of study drug in the non-randomized portion of the Maintenance Period.

ITT3-RES population: The subset of the ITT population who received at least one dose of ABBV-154 rescue therapy in the Maintenance Period.

The ITT Populations (including ITT1, ITT2, ITT3, ITT3-RN, ITT3-NRN populations) will be analyzed as randomized (i.e., according to the randomized/assigned treatment assignment).

Safety Populations

The safety population for the Induction Period (denoted by **SA1**) includes all subjects who received at least one dose of the study drug in the Induction Period.

The safety population for the Re-Induction Period (denoted by **SA2**) includes all subjects who received at least one dose of the study drug in the Re-Induction Period.

The safety population for the Maintenance Period (denoted by **SA3**) includes all subjects who received at least one dose of the study drug in the Maintenance Period.

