8.0 Handling of Potential Intercurrent Events for the Primary and Key Secondary Endpoints

Potential intercurrent events considered in the Study M20-371 include 1) premature discontinuation of study drug and 2) CD-related confounding medications defined in Section 8.1. As suggested by Qu et al. (2021), a mix of strategies will be used to handle different intercurrent events for the efficacy analysis.

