8.1 Intercurrent Event 1 (IE1): CD-Related Confounding Medications

The CD-related confounding medications intercurrent event is defined as follows.

In the Induction Period:

1. Initiation of protocol-defined Rescue Therapy for the Induction Period;
2. Initiation of glucocorticoids after Baseline of the Induction Period;
3. Fail to complete glucocorticoid taper by Week 6 of the Induction Period;
4. Initiation/increasing doses of aminosaliclates or immunomodulators.

In the Maintenance Period:

- Initiation of protocol-defined Rescue Therapy for the Maintenance Period.

Within each period, the time point of the CD-related confounding medications intercurrent event is defined as the date when one of the scenarios above occurs for a subject.

Binary endpoints: A composite strategy will be used in the efficacy analysis: the subject will be considered as non-responders at all visits on/after the CD-related confounding medications intercurrent event.

Continuous endpoints: A hypothetical strategy will be used in the efficacy analysis. Data collected on/after the initiation of CD-related confounding medications will not be used in the analysis. Efficacy analysis will be handled by using corresponding statistical models (e.g., the Mixed-Effect Model Repeated Measurement [MMRM] model).

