9.2.3 Additional Analyses

In addition, As Observed (AO) analysis will be performed as supplementary for categorical endpoints.

- AO: The AO analysis will not impute values for missing evaluations, and thus a subject who does not have an evaluation on a scheduled visit will be excluded from the AO analysis for that visit. AO will include all values collected in the study (except data collected after initiation of ABBV-154 rescue therapy for the analyses in the Maintenance Period).

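### The as-observed analysis of ABBV-154 rescue has no rule for add-on rescue medication and drops unevaluated subjects, so its response rates cannot fall below rates that count both as failures

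*SAP*

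**What the plan says.** SAP Section 9.8 sets out to evaluate ABBV-154 rescue on five measures at Weeks 12 and 24 after rescue: CDAI remission, SF/AP remission, CR100, mean FCP and mean hs-CRP. Its only method statement is that "the following endpoints will be analyzed on ITT3-RES population and AO analysis will be performed". ITT3-RES is defined in SAP Section 4.0 as "The subset of the ITT population who received at least one dose of ABBV-154 rescue therapy in the Maintenance Period".

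SAP Section 9.2.3 defines AO. Nothing is imputed: "a subject who does not have an evaluation on a scheduled visit will be excluded from the AO analysis for that visit". On what is kept, it says "AO will include all values collected in the study (except data collected after initiation of ABBV-154 rescue therapy for the analyses in the Maintenance Period"; the bracket closes there.

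On medication added later, SAP Section 2.2 says that subjects with at least 4 weeks of ABBV-154 rescue "who continue to demonstrate inadequate response may receive additional Rescue Therapy with oral glucocorticoids, aminosalicylates, or immunomodulators". Protocol Sections 4.1 and 5.4 say the same.

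The intercurrent-event rules are in SAP Section 8.0, titled "Handling of Potential Intercurrent Events for the Primary and Key Secondary Endpoints". For the Maintenance Period, the confounding-medication event in SAP Section 8.1 is "Initiation of protocol-defined Rescue Therapy for the Maintenance Period".

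**The concern.** With no control arm, the absolute response rate is the whole result of the rescue analysis. Protocol Section 4.2 gives the regimen a purpose: to see whether lost response can be recaptured. A subject who fails ABBV-154 rescue, adds a steroid and is in remission at Week 12 after rescue would be tabulated as recaptured by ABBV-154. A subject who withdraws before that visit would not be tabulated at all. Both features push the rate the same way.

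Elsewhere the SAP does otherwise: for binary endpoints in the Induction Period and the randomized part of the Maintenance Period, confounding medication makes the subject a non-responder and non-responder imputation is the main approach. What is at stake is how the rescue rates are read when later regimens are planned.

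**Working it through.** The plan gives no expected rate, sample size or power for the rescue analysis, so there is no stated figure to reproduce. The check is of the rules, then of direction, then of size on assumed inputs.

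**1. Does add-on medication come before the readouts?** It is allowed from 4 weeks after ABBV-154 rescue. The readouts are at 12 and 24 weeks, so it can start up to 12 − 4 = 8 or 24 − 4 = 20 weeks before them.

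**2. Does another rule catch it?**
- SAP 8.1: the Maintenance event is the start of rescue itself. Applied to ITT3-RES it would make every subject a non-responder. Add-on rescue is not a separate event.
- SAP 8.2: the rule for other Crohn's treatments is an exception within premature discontinuation of study drug. A subject adding a steroid on top of ABBV-154 has not discontinued.
- SAP 9.2.3: the only exclusion concerns data after ABBV-154 rescue, not data after add-on medication.
- SAP 7.3: drugs newly started after ABBV-154 rescue fall outside the Maintenance concomitant-medication definition, and no rescue-phase summary is defined. The tables would not show how many remissions followed an addition.

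**3. Direction (binary endpoints).** Let E be the eligible subjects, O those evaluated (all within E), R the observed responders, and R_a the responders whose evaluation falls on or after the start of add-on rescue. Then AO rate A = R/O, and the rate counting both as failures is (R − R_a)/E. With m = 1 − O/E and s = R_a/R:

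corrected rate = A × (1 − m) × (1 − s) ≤ A.

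No such ordering holds for mean FCP or hs-CRP.

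**4. Size, on assumptions only.** The number rescued, the missing fraction and add-on use are not in the documents. Taking A = 40%:

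| Missing m | s = 0 | s = 25% |
|---|---|---|
| 10% | 36% | 27% |
| 20% | 32% | 24% |
| 30% | 28% | 21% |
| 40% | 24% | 18% |

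For example, 0.40 × 0.80 × 0.75 = 24%. Over A from 30% to 50%, m from 10% to 40% and s from 0% to 40%, the corrected rate runs from 0.30 × 0.60 × 0.60 = 10.8% to 0.50 × 0.90 × 1 = 45%.

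**5. Who can reach the readouts?** Protocol 5.4 lets ABBV-154 rescue start from Maintenance Week 4 through Week 40. Within 40 weeks, the 12-week readout needs rescue by Week 40 − 12 = 28, and the 24-week readout by Week 40 − 24 = 16. The Maintenance schedule in Protocol Appendix D (a broken table in the text available) appears to place CDAI about every 8 weeks. On that reading, rescue at Week 8, 16 or 24 puts the 12-week readout at Week 20, 28 or 36, where no CDAI is scheduled.

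**The case against.** The strongest reply is that this is a descriptive summary of an uncontrolled cohort. No hypothesis is attached, Type I error control is not planned, and observed rates with stated denominators are a normal choice. SAP 9.5 also uses AO for the Re-Induction Period, which has no placebo arm. This stands as a limit on importance. It does not remove the gap: Protocol 5.4 does not permit Rescue Therapy in Re-Induction, whereas add-on rescue is part of the design after ABBV-154 rescue.

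A second reply is that non-responder imputation for every missing visit would overcorrect. This stands. Subjects rescued too late, or with no assessment scheduled near the readout, would become failures by design. The remedy has to be narrower.

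A reader might also infer that AO removes subjects who stop study drug for lack of efficacy. The documents do not support that. Protocol 5.6 encourages subjects who stop drug to keep attending scheduled visits; endoscopy is among the procedures waived, but no endpoint in SAP 9.8 is endoscopic. If evaluated, they stay in AO. Only withdrawals and missed evaluations leave the denominator.

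Finally, the AO exclusion of data after ABBV-154 rescue, read literally, would leave SAP 9.8 with no data. That cannot be intended, since SAP 9.8 asks for AO on exactly those data, but the two sections need reconciling.

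**Conclusion.** The point holds as a gap in an exploratory analysis, and its importance is low. As written, SAP 9.8 estimates response to ABBV-154 rescue plus any added medication, among those evaluated. For binary endpoints the AO rate cannot be below the rate counting add-on rescue and missing evaluations as failures, provided every evaluated subject belongs to the eligible set. The two are equal when there is neither missing data nor a response after add-on rescue.

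The size of the gap is unknown. Every percentage in the table rests on assumed missing-data and add-on rates, and none should be read as a forecast. A large bias may be tempting to infer, but the documents give nothing to support a particular size. Nor do they support extending the point to the primary or secondary endpoints, which have their own composite rule and imputation.

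**What to change.** In SAP 9.8:

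- Add an analysis of the binary endpoints in which visits on or after the start of protocol-defined add-on rescue count as non-response, in line with the composite strategy of SAP 8.1.
- Count missing as non-response only for subjects rescued by Maintenance Week 28 (12-week readout) or Week 16 (24-week readout) who had an assessment scheduled within a stated post-rescue window.
- For mean FCP and hs-CRP, also show results without data after add-on rescue.
- Report the numbers eligible, evaluable and with add-on rescue, and keep AO alongside.
- Reconcile the exclusion of post-rescue data in SAP 9.2.3 with SAP 9.8.

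The cost is SAP wording, one more table and probably a lower reported rescue rate. No new data collection is needed.

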All induction regimens in the study have an IV loading dose at Week 0 to enable faster achievement of steady-state levels, followed by SC doses administered EOW from Week 2 or every 4 weeks (E4W) at Week 4 and Week 8. The low induction regimen is expected to result in total antibody exposures that are comparable to the approved adalimumab CD dosing regimen, and additional efficacy is expected from the delivery of the GRM payload into activated immune cells. All selected induction regimens are adequately separated from each other with minimal overlapping exposures and cover a wide dose range to enable robust characterization of the dose/exposure-response relationship and selection of Phase 3 induction doses. The E4W regimen provides the optionality of exploring an alternate dosing frequency. The selected induction regimens are predicted to result in exposures that are similar to or lower than the maximum exposures safely tested in the ABBV-154 first-in-human study and are projected to be covered by adequate safety margins relative to no-observed-adverse-effect level exposures observed at a dose of 80 mg/kg/week SC in the 26-week Good Laboratory Practice -compliant toxicology study in cynomolgus monkeys. Projected ABBV-154 and payload safety margins for the highest induction dosing

regimen are at least 6×, based on predicted ABBV-154 human exposures and the observed toxicokinetic data in the 26-week cynomolgus monkey study.

For the Re-Induction Period, subjects will be re-randomized to the mid and high EOW induction dosing regimens to increase the chances of initial non-responders achieving clinical response AND/OR endoscopic response.

During the Maintenance Period, 2 dosing regimens of ABBV-154, 80 and 230 mg SC EOW will be evaluated which are equivalent to the EOW dose level of the low and mid doses during the Induction Period. The selected doses are expected to be sufficient to maintain response and to enable selection of Phase 3 maintenance doses.

Subjects who have an inadequate response at or after Week 4 in the Maintenance Period will be eligible to receive Rescue Therapy with a single dose of ABBV-154 600 mg IV followed by ABBV-154 230 mg SC EOW, to assess whether their response status can be recaptured.

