Subjects who receive protocol-defined glucocorticoid Rescue Therapy, initiate glucocorticoids (other than inhaled) after Baseline without qualifying for Rescue Therapy, fail to complete glucocorticoid tapering by Week 6, or who increase doses of or initiate treatment with aminosaliculates or immunomodulators during the Induction Period will be considered non-responders and will be re-randomized into the Re-Induction Period. All subjects who fulfill the clinical response AND/OR endoscopic response (per local read) definition at Week 12 of the Re-Induction Period will be re-randomized into the Maintenance Period.

The criteria for inadequate response are the following:

- Induction Period: Presence of clinical symptoms defined as CDAI ≥ 220 and not achieving a decrease in CDAI ≥ 35 points from Baseline of the Induction Period.
- Maintenance Period: Presence of clinical symptoms defined as CDAI ≥ 220 and an increase in CDAI ≥ 70 points from Baseline of the Maintenance Period.
- And, for both the Induction Period and Maintenance Period, presence of at least 1 of the following objective markers of inflammation:
 - hs-CRP \geq ULN, and worse than the lowest value assessed during the study, or
 - FCP ≥ 250 $\mu\text{g/g}$, and worse than the lowest value assessed during the study, or
 - SES-CD, excluding the narrowing component, ≥ 6 (≥ 4 for isolated ileal disease), as scored by the site investigator at an endoscopy.

The last available values for hs-CRP and FCP will be used for assessment of inadequate response.

Use of Rescue Therapy in subjects who qualify is at the investigator's discretion and not mandatory.

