3.0 Endpoints

In Section 3.0, please note

1. "Baseline" refers to the last available measurement on/before Baseline [Week 0, Day 1] of the Induction Period;
2. All endoscopic endpoints will be scored by central review;
3. Average daily liquid or very soft stool frequency (SF) and average daily abdominal pain (AP) score (SF/AP)-based efficacy endpoints will be analyzed in

the subset of subjects with an average daily liquid or very soft SF score ≥ 4 and/or average daily AP score ≥ 2 at Baseline.

The following endpoint definitions apply to the efficacy variables described below:

- **Endoscopic response:** decrease in Simple Endoscopic Score for Crohn's Disease (SES-CD) $> 50\%$ from Baseline (or for subjects with isolated ileal disease and a Baseline SES-CD of 4, at least a 2-point reduction from Baseline)
- **Clinical remission per CDAI:** CDAI < 150
- **Clinical response (CR100):** a decrease of CDAI ≥ 100 points from Baseline
- **Clinical remission per SF/AP:** average daily very soft or liquid SF ≤ 2.8 and not worse than Baseline AND average daily AP score ≤ 1 and not worse than Baseline
- **Enhanced Clinical Response per SF/AP:** $\geq 60\%$ decrease in average daily very soft or liquid SF and/or $\geq 35\%$ decrease in average daily AP score and both not worse than baseline, and/or clinical remission per SF/AP
- **Clinical response per SF/AP:** $\geq 30\%$ decrease in average daily liquid or very soft SF and/or $\geq 30\%$ decrease in average daily AP score and both not worse than Baseline
- **Endoscopic remission:** SES-CD ≤ 4 and at least a 2-point reduction versus Baseline and no subscore > 1 in any individual variable
- **Ulcer-free endoscopy:** SES-CD ulcerated surface subscore of 0 in subjects with SES-CD ulcerated surface subscore ≥ 1 at Baseline

Details of CDAI, SES-CD and patient-reported outcome (PRO) questionnaires are provided in [Appendix B](#), [Appendix C](#) and [Appendix D](#) respectively.

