9.0 Efficacy Analyses

9.1 General Considerations

All efficacy analyses will be conducted in the ITT Populations in each period. All tests will be 2-sided at an alpha level of 0.1.

For all efficacy endpoints, the descriptive statistics will be provided by treatment group for each of the study period. The statistics include number of observations, mean, standard deviation, 95% CI, minimum, median, and maximum for continuous variables, and number, percent and two-sided 95% CI for discrete variables. And number of subjects with missing data due to COVID-19 pandemic will be summarized for primary and secondary efficacy endpoints.

Unless otherwise specified, any subject will be analyzed according to the actual stratum the subject belongs to.

The Primary Analysis for the Induction Period and Re-Induction Period will be performed after all subjects have completed Week 12 of the Induction Period and Re-Induction Period, respectively, or prematurely discontinued study participation. This is the final efficacy analysis for the Induction Period and Re-Induction Period, respectively.

The final analysis will be conducted after all subjects have completed Week 40 of the Maintenance Period plus the 70 day Follow-up Visit or prematurely discontinued study participation. This is the final efficacy analysis for the Maintenance Period. To ensure the

integrity of the trial, the study sites and subjects will remain blinded until the final database lock is completed.

In Section 9.0, "Baseline" refers to the last non-missing observation prior to the first administration of study drug in the Induction Period, unless specified otherwise. "Comparison of treatment groups" refers to (i) comparison of each ABBV-154 group and placebo group in the Induction Period; (ii) comparison of Re-Induction Group 2 and Re-Induction Group 1 in the Re-Induction Period; (iii) comparison of each ABBV-154 group and placebo group for the randomized portion in the Maintenance Period.

"Stratification factors for the corresponding period" refers to randomization stratification factors specified in Section 2.3 except for the Maintenance Period, the randomization stratification factors used in efficacy analyses for the Maintenance Period are

- Achievement of CR100 at entry of the Maintenance Period (Week 12 of the Induction/Re-Induction Period): Yes vs No;
- Entry to the Maintenance Period: Induction Period vs Re-Induction Period.

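### CR100 after ABBV-154 rescue (SAP 9.8) counts subjects who still met CR100 when rescued, so the rate mixes response never lost with response recaptured

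*SAP*

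**What the plan says.** SAP 9.8 lists among the rescue endpoints "Achievement of CR100 at Week 12 and Week 24 after ABBV-154 rescue therapy". SAP 3.0 defines CR100 as "a decrease of CDAI ≥ 100 points from Baseline", where Baseline "refers to the last available measurement on/before Baseline [Week 0, Day 1] of the Induction Period". For all of SAP Section 9, which includes 9.8, SAP 9.1 says that Baseline "refers to the last non-missing observation prior to the first administration of study drug in the Induction Period, unless specified otherwise". SAP 9.8 specifies no other reference, so CR100 after rescue is a fall of at least 100 points from the value before any study drug.

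The analysis set is ITT3-RES (SAP 4.0): every subject with at least one ABBV-154 rescue dose in Maintenance. The analysis is as observed. SAP 9.8 neither excludes nor separately counts subjects who met CR100 when rescued.

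Protocol 5.4 sets the Maintenance criteria for inadequate response: "Presence of clinical symptoms defined as CDAI ≥ 220 and an increase in CDAI ≥ 70 points from Baseline of the Maintenance Period", together with "presence of at least 1 of the following objective markers of inflammation". The markers are hs-CRP, FCP and SES-CD. None of the criteria compares CDAI with the Induction Baseline.

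Protocol 4.2 gives the purpose of ABBV-154 rescue: "to assess whether their response status can be recaptured".

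**The concern.** Entry to the rescue analysis and success in it use different reference points. Entry depends on a rise from the Maintenance Baseline; success depends on a fall from the Induction Baseline. A subject who responded strongly in Induction can worsen by 70 points and still be more than 100 points below the Induction Baseline. Such a subject meets the success criterion before the rescue dose and is counted as a success later if CDAI merely stays where it is.

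A response that was not lost cannot be recaptured. Everyone in ITT3-RES received rescue and SAP 9.8 names no comparator, so a reader of the CR100 rate has only the state before rescue to set it against, and SAP 9.8 does not report that state. The rate could make rescue look more effective at restoring response than it is, mainly through subjects with a high Induction Baseline CDAI.

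**Working it through.** The plan states no figure for this analysis, so there is none to reproduce. The check is algebra on the CDAI thresholds, followed by a simulation under stated assumptions.

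**Inputs.** B = Induction Baseline CDAI, eligible range 220 to 450 (Protocol 5.1, criterion 6). M = Maintenance Baseline CDAI. R = CDAI at rescue.

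**Conditions.**
- Rescue, CDAI part (Protocol 5.4): R ≥ 220 and R ≥ M + 70.
- CR100 still met at rescue (SAP 3.0): R ≤ B − 100.
- Both hold when max(220, M + 70) ≤ R ≤ B − 100.
- Such an R exists only if B − 100 ≥ 220, so B ≥ 320, and B − 100 ≥ M + 70, so M ≤ B − 170.

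**Cases.**

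| B | M | R | R − M | B − R | CDAI part of rescue met | CR100 at rescue |
|---|---|---|---|---|---|---|
| 420 | 200 | 270 | 70 | 150 | yes | yes |
| 400 | 180 | 260 | 80 | 140 | yes | yes |
| 450 | 280 | 350 | 70 | 100 | yes | yes (limit) |
| 320 | 150 | 220 | 70 | 100 | yes | yes (limit) |
| 310 | 140 | 220 | 80 | 90 | yes | no |

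Overlap is therefore possible for B from 320 to 450, inside the eligible range, and impossible below 320.

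**Subjects who entered on endoscopic response alone.** Without CR100 at entry, M > B − 100. Rescue then needs R ≥ M + 70 > B − 30, so the fall from the Induction Baseline is under 30 points and overlap is impossible.

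**Size, by assumption.** The documents give no CDAI distributions. Assume B normal with mean 290 to 330 and SD 60, limited to 220–450; fall to Maintenance entry with mean 100 to 180 and SD 70; CR100 met at entry; rescue at max(220, M + 70) plus an overshoot that is zero or exponential. The ranges cover nine combinations of means, and both setting simulated negative entry scores to zero and dropping them.

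| Mean overshoot | Still CR100 at rescue |
|---|---|
| 0 (exactly at threshold) | 11%–38% |
| 30 points | 5%–21% |
| 60 points | 3%–14% |

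Two variants model the rise itself and keep only subjects who qualify:
- same B and fall, rise with mean 60 and SD 80: 3%–14%;
- B with mean 300–340 (SD 50–60), M with mean 120–180 (SD 60), rise with mean 60–140 (SD 70–80): about 5%–30%.

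All of these are shares of rescued subjects who entered with CR100. The share of ITT3-RES is this figure times the fraction of ITT3-RES that entered with CR100, so it is lower.

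**An alternative endpoint, tested.** Suppose CR100 were replaced by a fall of at least 100 points from R. A subject at 300, 150 at entry, 225 at rescue and 150 again afterwards lost CR100 (300 − 225 = 75) and regained it (300 − 150 = 150), yet fell only 75 points from rescue and would fail. Under the first set of assumptions, the share of CR100 entrants who would fail even after full return to their entry CDAI is 44%–80% at threshold, 24%–47% with mean overshoot 30 and 14%–29% with mean overshoot 60. At each overshoot the lowest of these exceeds the largest overlap.

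**The case against.** The strongest reply is that the reference point is right. Protocol 3.4 and SAP 3.0 and 9.1 use the Induction Baseline in every period, and the trial's clinical response status is CR100 against it. Being in that status again is the natural meaning of recapture. This stands. A reader might infer that the Induction Baseline is the wrong reference for rescue and that CDAI at rescue should replace it. The documents do not support that, and the replacement would fail subjects who return fully to their entry CDAI. The gap is narrower: status at rescue is not reported.

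SAP 9.8 speaks only of evaluating efficacy and never labels these subjects as recaptured. That is also true. The word comes from Protocol 4.2, but 4.2 states what rescue is for, so the rate will be read against it.

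The size can be pushed down. The highest shares need rescue exactly at threshold. Subjects in the overlap had the deepest falls, and those with M below 150 need a rise of more than 70 to reach 220. Nor is success certain for them: they are worsening, and some sit at the CR100 margin. All of this stands and is why only a range is given.

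Finally, this is an as-observed summary of a post-randomisation subset, with no comparison or test specified. That limits the weight of the point but does not remove it.

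The FCP and hs-CRP items might seem to share the fault. They do not: SAP 9.8 asks for means, which involve no Baseline.

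**Conclusion.** The point holds, with minor weight. The documents' own thresholds allow a subject with Induction Baseline CDAI of at least 320 and a Maintenance-entry value at least 170 points lower to qualify for rescue on CDAI while meeting CR100, and SAP 9.8 would count that subject as a success if CR100 still holds at Week 12 or 24. That follows from the text and needs no assumption.

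How many subjects are affected does rest on assumptions: roughly 3% to 38% of rescued subjects who entered with CR100. A reader might take the upper figure as the amount by which the reported rate is inflated. It is not, because it is a share of CR100 entrants under assumed distributions and not all of those subjects would end as successes.

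CDAI remission after rescue (below 150) is unaffected, because rescue requires at least 220. A reader might also infer a fault in the rescue criteria; none is shown, and the point concerns only how the outcome is reported.

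**What to change.** In SAP 9.8, before database lock:

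- keep CR100 against the Induction Baseline;
- tabulate CR100 status at the last CDAI on or before the first ABBV-154 rescue dose;
- report CR100 at Weeks 12 and 24 after rescue among subjects not meeting CR100 at that point, and give their number.

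Do not substitute a fall of at least 100 points from CDAI at rescue.

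The cost is SAP wording and one extra table. CDAI is already needed to establish inadequate response, including at unscheduled visits (Protocol 5.4), so no new data are required. The denominator will be smaller and the reported rate possibly lower. No change to the rescue criteria is proposed.
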